The proposed study is relevant in preventing unsafe sex practices and the associated high risk with STIs, which is an alarming issue among Hong Kong youths. Given the increasing trend of premarital sex and inconsistent condom use among Hong Kong college students, there is an urge to provide comprehensive STIs risk reduction intervention with a focus on addressing sexual coercion for females.

This study would enable evaluation of the acceptability of ICBI in sexual health education and improve STIs risk reduction intervention to advocate safe sexual behaviors among college population. Such cost-effective intervention could be translated as part of the student service to empower young females with the knowledge about sexual coercion and sexual consent as well as promoting safe sexual practices on university campus.

5. Study Design

Design

A multi-centred randomized controlled trial (RCT) design as recommended by the Cochrane review for evaluating the sexual health intervention effect.[9]

Subjects and setting

Female university students (n = 500), across disciplines and year of study, will be recruited from five universities with dormitory or residential halls in Hong Kong. The eligibility criteria are listed below.

The inclusion criteria are:

- Female university students aged at least 18 years

- Able to read Chinese or understand Cantonese
- Unmarried
- Having intimate partners in the past 12 months
- Did not receive any sexual health information including formal face-to-face or online education/ training courses related to contraceptives and sexually transmitted diseases from university, hospitals, clinics and non-governmental organizations in the past 12 months

The exclusion criteria are:

- Unwilling to complete the questionnaires at 3 time points
- Pregnant women and postnatal women
- With psychiatric illness

Interactive Computer-Based Intervention (ICBI)

The ICBI will be conducted based on Health Belief Model (HBM)[20] and the Continuum of Conflict and Control (CCC).[21] HBM is selected because it was found to be effective in adopting safer sex practice in previous studies[9, 10]. CCC is selected because it emphasizes on level of violence and indicates that sexual coercion can occur without physical violence and with minimal fear, which strengthen the knowledge about sexual coercion and sexual consent of condom use and sex refusal. There are 4 components of the ICBI which will be delivered in 3 phases:

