Participants will be asked to complete the web-based baseline survey at enrolment. The *web-based questionnaire* will be set up under an online platform. Participants may use their mobile devices including laptop computers and smartphones to complete the questionnaire. Participation is entirely voluntary. Written informed consent will be obtained via the web-based platform before completing the baseline questionnaire.

After completion of the questionnaire, the recruited students will then be randomized to either intervention group or control group, according to a list prepared by blocked randomization of a size decided by a *randomizer*. The block size and order of allocation will be kept securely in the randomizer to avoid selection bias. Allocation concealment will be done at the online platform according to the participants' enrolment sequence. The participant will then be guided to a web-page according to their group allocation.

At 3-month and 6-month after the entry of the study, participants will receive a link through their e-mail to complete a follow-up questionnaire (T2). Three months later, another e-mail link will be sent to participants for completing the last follow-up questionnaire (T3). If no response from a participant, a follow up telephone text-message and/or telephone call will be sent after 1 week as a reminder.

6. Treatment of Subjects

Not applicable

7. Assessment of Efficacy

Not applicable

8. Assessment of Safety

There is no question designed to provoke a strong or emotional reaction. If the participants find the intervention stressful or discomfort or having anxious physiological responses (for example, trembling, shaking, sweating, facial flushing, severe headache, shortness of breath, palpitations, severe pain or crying uncontrollably), they will be given the opportunity to decide whether to continue or to terminate the intervention and withdraw from the study.

9. Statistics

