To assess the efficacy of ICBI in increasing consistency of condom use, a linear mixed effects model will be adopted with intervention group and baseline consistency of condom use as the covariates. The group by time interaction shall be assessed for changes of ICBI effects over time. The mixed effects model was to take account of the extra covariance of repeated measurements at 3 and 6 months. The intention-to-treat principle will be adopted and all study subjects will be included in the analysis. Missing values at 3- and 6-month follow-up will be replaced by the last observed value and multiple imputation. The analysis will be repeated on the per-protocol set comprising individuals without missing values.

For secondary outcomes that were assessed approximately on a continuous scale, the same analysis approach as mentioned above will be adopted. For those assessed on a dichotomous scale, e.g. sexual coercion, similar approach by a non-linear mixed effects model with a logit link will be used.

The analysis will be performed by using the IBM SPSS (IBM Corp, Armonk, NY, USA). Each estimated effect will be accompanied by a 95% confidence interval and 5% level of significance.

10. Direct Access to Source Data/ Documents

The investigators and the research assistants of the research team are responsible for data collection and they will be permitted to access to source data and study record.

11. Quality Control and Quality Assurance

Daily logs will be recorded by the research assistants to monitor the study progress including the number of respondents approached, interviews completed or refused and incomplete interviews. All data entered in the database will be verified and cleaned. After completion of data entry, computer logic checks will be run for consistency of related code. Necessary corrections will be made to the database.

12. Ethics

The protocol will be submitted to the Institutional Review Board of the University of Hong Kong/ Hospital Authority Hong Kong West Cluster for approval. The conduct of the study will be complied to the “Declaration of Helsinki”. Participation in the study is voluntary. An information sheet is provided and a written consent is required from the participant for each individual study.

13. Data Handling and Record Keeping

The completed questionnaires and records will be kept by the Principal Investigator for 10 years. The computerized data will be kept for planning of future studies.

14. Financing and Insurance

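### University is neither a named randomisation stratum nor a model term in this five-university trial: a small, avoidable loss of precision and balance, with no effect on validity

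*Combined protocol and SAP*

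**What the plan says.** Section 5 (Design) describes "A multi-centred randomized controlled trial (RCT) design". Under Subjects and setting it states: "Female university students (n = 500), across disciplines and year of study, will be recruited from five universities".

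Under Procedures in the same section, participants are allocated after the baseline questionnaire "according to a list prepared by blocked randomization of a size decided by a" randomiser, and "Allocation concealment will be done at the online platform according to the participants' enrolment sequence". No stratification factor is named. The text does not say whether the sequence runs across all universities or within each one; a single list across all of them is the natural reading.

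Section 9 states that "a linear mixed effects model will be adopted with intervention group and baseline consistency of condom use as the covariates", with a group by time interaction. The reason given for the mixed structure is repeated measurement: "The mixed effects model was to take account of the extra covariance of repeated measurements at 3 and 6 months". No site effect is mentioned. Continuous secondary outcomes follow the same approach, and dichotomous ones use a logit link.

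The demographic items listed in Section 5 (Measurements) do not include university, although that list is open-ended.

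**The concern.** In a trial recruiting at several sites, site is a baseline factor that may predict the outcome. If condom use differs between universities beyond what the baseline measure captures, leaving university out of the model keeps that difference in the error variance. Leaving it out of the randomisation lets the arms differ by chance in their mix of universities.

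What is at stake is the width of the confidence interval and the look of the baseline table. There is also a question of discretion: Section 9 is silent on university, so if a visible imbalance arose, any later decision to adjust or not would be post hoc.

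**Working it through.** **Inputs from the documents.** N = 500 and five universities (Section 5, Subjects and setting); a blocked list with no stratum (Section 5, Procedures); model terms group, baseline consistency of condom use, and group by time (Section 9). The plan gives no effect size, SD, power or dropout rate behind the 500, so it has no figure of its own to reproduce.

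**Assumptions.** 250 per arm (the allocation ratio is not stated); 100 women per university unless noted; one list across universities; a single follow-up time point; residual outcome variance after baseline adjustment set to 1, of which a share ICC lies between universities, with ICC from 0.01 to 0.05.

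**1. Chance imbalance.** With 250 of 500 allocated to each arm, the number in the intervention arm at a site of 100 is hypergeometric.
- P(one given site splits 60:40 or worse) = 3.3%.
- P(at least one of five does), from the joint distribution = 14.6%.
- A simulation with blocks of 4 and randomly varying site sizes gives 13.3%.
- With unequal shares, assumed at 40/25/15/12/8%, the figure rises to 33% (blocks of 4, random sizes) or 40% (fixed sizes, no small blocks).

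**2. What such an imbalance does to the estimate.** Suppose one site splits 60:40 and lies one between-site SD from the rest.
- Shift = (60/250 - 40/250) x sqrt(ICC) = 0.08 x sqrt(ICC).
- ICC 0.01: 0.08 x 0.100 = 0.008 SD. ICC 0.05: 0.08 x 0.224 = 0.018 SD.
- Standard error of the group difference = sqrt(4/500) = 0.089 SD.

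The shift is small against the standard error, which already allows for it on average. Steps 2 and 3 therefore describe largely the same cost.

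**3. Precision.** The part of the site effects common to all five sites cancels between arms, so only (5 - 1)/5 = 0.8 of the ICC is removable.
- Variance per woman without the term: (1 - ICC) + 0.8 x ICC = 1 - 0.2 x ICC.
- With the term and a stratified list: 1 - ICC.
- With the term but no stratified list: (1 - ICC) x 1.008. The 0.8% is the cost of estimating four site parameters when sites are not balanced by arm.
- Extra women = 500 x (variance without / variance with - 1).

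| Residual ICC | Stratify and adjust | Adjust only |
|---|---|---|
| 0.01 | 500 x (0.998/0.990 - 1) = 4 | 500 x (0.998/0.99792 - 1) = 0 |
| 0.05 | 500 x (0.990/0.950 - 1) = 21 | 500 x (0.990/0.9576 - 1) = 17 |

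For a comparison with exactly 80% power without the term, power when stratifying and adjusting is Phi(2.802 x sqrt(variance ratio) - 1.960). This gives 80.3% at ICC 0.01 (ratio 1.0081) and 81.6% at ICC 0.05 (ratio 1.0421).

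**4. Validity.** In simulated trials with an unstratified list, blocks of 4 and no university term (4,000 runs per setting, ICC 0.02, 0.05 and 0.10), the two-sided 5% test rejected a true null in 4.5% to 5.2% of runs, and the estimates were unbiased.

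**5. Dichotomous outcomes.** In a logistic check (300 runs, single time point, about 13% prevalence, assumed site SD 0.4), adding university raised the mean standard error of the log odds ratio from 0.291 to 0.295, and raised it in every run. The gain in step 3 does not carry over to the logit models.

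**The case against.** The strongest reply is that centre matters less here than usual. Both arms receive a website, and consent, allocation and follow-up are online. No site staff deliver the intervention or assess outcomes, so the universities act mainly as sources of recruits. The model also adjusts for baseline consistency of condom use, which absorbs stable differences between universities on the primary outcome. The residual ICC may therefore sit at or below the low end of the assumed range, where adjusting without stratifying gains nothing. All of this stands, and it is why the point is minor.

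A reader might draw four stronger conclusions that the documents do not support:
- **The omission biases the result or makes the test anticonservative.** Students, not universities, are randomised, and step 4 shows neither effect.
- **All between-university variation remains in the error.** Only the part not explained by baseline condom use does.
- **University is already known at enrolment, so the change is free.** No section says it is recorded. The enrolment form may hold it, but that is an assumption.
- **Adding university tightens every interval.** This is not so for outcomes analysed with a logit link.

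It is also possible that the list was stratified and the protocol does not say so. In that case the text needs a clarifying line, and the model should still carry the stratum.

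**Conclusion.** The omission is real: university is neither a named stratum nor a model term in a trial that describes itself as multi-centred. The consequence is a modest loss of efficiency and an avoidable chance imbalance, not a threat to validity. For a residual ICC of 0.01 to 0.05, stratifying plus adjusting is worth about 4 to 21 women out of 500, and adjusting alone about 0 to 17. The chance that at least one of five equal sites splits 60:40 or worse is about 14-15%, and higher if recruitment is uneven.

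These sizes rest on 250 per arm, one list across universities, a single time point, and an ICC range that is assumed. The point is a worthwhile improvement because it costs so little; the trial does not depend on it.

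**What to change.** 1. Section 5 (Measurements and Procedures): state that university is recorded at online enrolment, before randomisation.
2. Section 5 (Procedures): run the blocked list separately within each university, with block sizes still concealed. If this is already done, say so.
3. Section 9: add university as a five-level fixed effect to the linear mixed models for the primary and continuous secondary outcomes. A fixed effect is preferable because five sites are few for estimating a random-effect variance.
4. Section 9, dichotomous outcomes: if university is added for consistency with the stratification, state that the odds ratio is then conditional on university, and do not present the change as narrowing the interval.
5. If randomisation is already complete, prespecify the fixed effect alone, before outcome data are examined by arm.

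The cost is one enrolment field, one randomiser setting and four model parameters. The downside is essentially no net gain if the universities barely differ and the list is not stratified.

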For the control group, all participants will receive minimal intervention with a one-page online information about procedures and tips of condom use. The site for control group will have similar graphic design as that for intervention group. However, there will be no self-assessment materials or online quiz questions. The time spent on the web information will approximately be 30 minutes for intervention group and 10 minutes for control group.

It is hypothesized that female students in the intervention group will have consistent condom use at 3- and 6-month follow-up compared to students in the control group. It is expected that the intervention will provide participants with increased knowledge,

attitude, norms, self-efficacy towards condom use, sexual consent and sexual coercion.

Measurements

The following measurements will be conducted at 3 time points: baseline (T1); 3-month post intervention (T2); and 6-month post intervention (T3), which consist of the same set of measurements. The individual characteristics will also be assessed at T1 and questions related to feasibility of the programme will be asked only at T3.

Primary outcomes

1. Change from Consistency in condom use with every partner: It will be assessed by using percentage of male condom protected sex with every partner according to the recommended guidelines from the systematic review of 56 studies.[22] Other behavioural items will also be asked, for examples, condom use at last sex and description of sexual partners (dating partner vs casual partner) at last sex.

Secondary outcomes:

- 2. Knowledge, attitude, norms and self-efficacy of condom use:** It will be assessed by 25-item MCAS[23] which contains assessment on five subscales: reliability and effectiveness of condoms, sexual pleasure associated with condom use, stigma associated with people proposing or using condoms, embarrassment about negotiating and using of condoms, and embarrassment about purchasing condoms. The measurement can be used with participants who do and do not have personal experience with condoms. The items are answered by a 7-point Likert-scale and total scores are ranged from 7 to 175. The higher the score, the more positive is the knowledge, attitude, norms, and self-efficacy of condom use.

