- 3. Knowledge, attitude, norms and self-efficacy of sexual coercion and sexual consent:** It will be assessed by 39-item SCS-R.[24] It contains four attitudinal subscales (positive attitude towards establishing consent, lack of perceived behavioral control, relationship length norms, and (pro) assuming consent) and two behavioral subscales (indirect consent behaviors and awareness of consent). It is suitable for both participants who do and do not have personal

experience with sexual consent. The items are answered by a 7-point Likert-scale and total scores are ranged from 39 to 273. The higher the score, the more positive is the attitude, norms, and perceived behavioural control of sexual consent.

4. **Sexual coercion:** It will be measured by 7-item subscale from Revised Conflict Tactic Scale.[25] The responses will be on a dichotomous scale for assessing sexual coercion. All items will be rated on a 7-point Likert scale indicating how often the behaviour occurred. The higher the score, the greater the frequency.
5. **Self-efficacy in sexual communication:** It will be assessed by 20-item SCSES.[26] It contains five domains (contraceptive communication, positive sexual messages, negative sexual messages, sexual history, and condom negotiation). The items are answered by a 4-point Likert-scale and total scores are ranged from 20 to 80. The higher the score, the more the self-efficacy in sexual communication.
6. **Retention of the participant:** It will be evaluated by recording retention of the participants at 6-month post intervention.
7. **Engagement time of the participants:** It will be evaluated by recording the total time spent on the website at 6-month post intervention.
8. **Incidence of adverse events of the intervention:** It will be evaluated by recording the adverse events of the intervention at 6-month post intervention.
9. **Overall satisfaction of the intervention:** It will be evaluated by recording overall satisfaction of the intervention in a scale of 0-10 and overall perception of the intervention with a 5-Likert-scale. Also, participants will be asked whether they will recommend the intervention to friends and “yes” will be scored 1 point. The higher the score, the higher overall satisfaction of the intervention.
10. **Total pages of the website each participant visited:** It will be evaluated by recording the total pages of the website each participant visited.

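### Section 8 ties stopping the website to leaving the study, so a distressed woman who stops has no observed 3- or 6-month outcomes for the promised intention-to-treat analysis

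*Combined protocol and SAP*

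**What the plan says.** Section 8 (Assessment of Safety) covers participants who find the intervention stressful or have anxious physical reactions to it. It gives them the chance "to decide whether to continue or to terminate the intervention and withdraw from the study". Two courses are named, and the second joins ending exposure with ending participation.

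Section 9 (Statistics) states: "The intention-to-treat principle will be adopted and all study subjects will be included in the analysis". It continues: "Missing values at 3- and 6-month follow-up will be replaced by the last observed value and multiple imputation". It then adds: "The analysis will be repeated on the per-protocol set comprising individuals without missing values".

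Section 5 (Study Design) describes the two sites: "The time spent on the web information will approximately be 30 minutes for intervention group and 10 minutes for control group". The intervention site has personal risk results, narrative videos and self-assessment; the control site is a single page without self-assessment or quiz. Outcomes come from questionnaires linked by e-mail at 3 and 6 months, with a reminder after one week to those who do not respond.

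Two secondary outcomes in Section 5 also depend on who remains in the study. On adverse events: "It will be evaluated by recording the adverse events of the intervention at 6-month post intervention". On retention: "It will be evaluated by recording retention of the participants at 6-month post intervention".

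Section 6 (Treatment of Subjects) is marked not applicable. No section describes a woman who stops the website but stays in follow-up.

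**The concern.** Exposure is a short online session, and the outcomes are questionnaires months later. Being unable to finish a video does not prevent a woman from answering them. Under the wording of Section 8, however, the only stated alternative to continuing is to leave the study. Outcomes that could have been observed are then missing by rule.

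Three things are at stake. First, the intention-to-treat result would rest on assumptions for exactly the women who reacted badly to the assigned material, and this loss is plausibly more frequent in the arm with the longer, interactive content. Second, the women most likely to report an adverse event may be absent when events are recorded at 6 months. Third, stopping the website is counted as study drop-out in the retention outcome, so that outcome mixes two different events.

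**Working it through.** The protocol gives no figure to reproduce. The sample of 500 comes without a stated power, effect size, standard deviation, dropout rate or distress rate. The check is therefore a trace of the data, followed by arithmetic on assumed rates for scale.

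**1. What happens to one woman.** She completes baseline, is randomised, becomes distressed while viewing the site, and takes the second option. If this is before T2, baseline is her only value.

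- The mixed model uses baseline as a covariate and the 3- and 6-month values as outcomes. Without imputation she contributes no outcome.
- Carrying the last value forward assigns her no change from baseline.
- Multiple imputation in its usual form predicts her values from women who stayed, assuming data missing at random. That is doubtful when the assigned content caused the loss.
- The per-protocol set excludes her, because it requires complete values.

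She is thus included in the primary analysis, but without any observed outcome.

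**2. Primary outcome, for scale.** Assumptions: 250 women per arm (500 / 2; the allocation ratio is not stated), and distress withdrawals in the intervention arm only. Let d be the share of that arm withdrawn and D the error in the mean of their filled-in values, in percentage points of condom-protected sex. Bias in the arm difference = d x D.

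| d (women of 250) | D = 5 | D = 10 | D = 20 |
|---|---|---|---|
| 1% (2.5) | 0.05 | 0.10 | 0.20 |
| 2% (5) | 0.10 | 0.20 | 0.40 |
| 5% (12.5) | 0.25 | 0.50 | 1.00 |
| 10% (25) | 0.50 | 1.00 | 2.00 |

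The sign of D is not known. Under carry-forward, D is about 0 if these women already used condoms less at baseline and did not change. The intervention arm is flattered if they would have got worse, and penalised if they would have improved.

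**3. Per-protocol repeat.** Suppose withdrawn women average 20 points below the rest. Completers then overstate the raw arm mean by 20d, which is 1.0 point at d = 5%. If that deficit was already present at baseline, adjustment with slope b leaves 20d(1 - b). With an assumed b = 0.6 this is 20 x 0.05 x 0.4 = 0.4 points.

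**4. Adverse events.** Let p be the true rate and w the share of affected women who withdraw, with events captured only from women still in follow-up. Rate seen at 6 months = p(1 - w) / (1 - pw). For p = 5% and w = 50%: 0.025 / 0.975 = 2.6%.

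| True rate | w = 25% | w = 50% | w = 100% |
|---|---|---|---|
| 2% | 1.5% | 1.0% | 0% |
| 5% | 3.8% | 2.6% | 0% |
| 10% | 7.7% | 5.3% | 0% |

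**5. Retention.** Each percentage point of an arm that leaves this way lowers that arm's retention by one point, even if the women would have answered T2 and T3.

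**The case against.** The strongest reply is that Section 8 states a participant's right and does not order follow-up to end for everyone who leaves the site. Engagement time, pages visited and task performance are secondary outcomes, so partial use is expected. Links and reminders are not conditional on finishing the site, and the per-protocol set is defined by missing values, not by website use. This stands: a reader might infer that any woman who closes a video is withdrawn, and the protocol does not say so. The point concerns only a distressed woman who takes the stated exit, and some of those women may want no further contact.

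A second reply is that Section 9 fills in missing values and adjusts for baseline. This also stands against a stronger reading. A reader might infer that these women are deleted from the primary analysis and that the intervention is therefore flattered by 0.4 to 2.0 points (a 20-point deficit with 2-10% leaving). That arithmetic describes a completers-only comparison of raw means on chosen rates, not the planned primary analysis. What the reply does not show is that imputation makes up for outcomes that could have been observed.

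Third, it is an inference from content and duration that exits fall mainly in the intervention arm. The coercion scale and the childhood-abuse item are asked before randomisation, and the coercion scale is repeated in both arms, so distress from questions is not specific to one arm. Finally, the information sheet mentioned in Section 12 was not in the text reviewed and may set out withdrawal terms.

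**Conclusion.** The point holds in limited form. Section 8 makes study withdrawal part of stopping the website, and no visible text keeps T2 and T3 collection open for a woman who stops in distress. That sits badly with the Section 9 commitment to analyse all subjects by intention to treat.

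The documents do not support a claim of material bias in condom use in a known direction. No distress or dropout rate is given, the sign depends on how these women would have changed, and the effect is probably small unless such withdrawals are common. The possible loss from the adverse-event record is proportionally larger, but only if events are captured solely from women still in follow-up, which Section 5 leaves open. The effect on retention follows directly from the wording. The reason to change the text is that obtainable data would be replaced by assumptions at almost no saving.

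**What to change.** Reconcile Section 8 with Section 9 and with the adverse-event and retention outcomes in Section 5, for data collection only:

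- State that stopping the website does not by itself end outcome collection. T2 and T3 links continue unless the woman separately declines further contact, and she is offered that choice at the time she stops.
- Record stopping the website and withdrawing from follow-up as separate events, each with its reason. Count only the second against retention.
- State that observed follow-up data from women who stopped the website enter the intention-to-treat analysis.
- Say whether adverse events are recorded when they occur, including for women who then withdraw.
- Make the information sheet match.

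A woman's right to stop or to withdraw is unchanged. The cost is a few sentences in the protocol, matching wording in the information sheet, and a two-option button on the site; no extra visits or participants are needed. The downside is that some women who stopped in distress will be sent the questionnaires again, including the coercion items, unless they decline. That is why the choice should be offered at the moment of stopping.

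### Does Section 9 test a group-by-time interaction in a model that has no time term?

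*Combined protocol and SAP*

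**What the plan says.** Section 9 (Statistics) describes the primary analysis in a few sentences. For consistency of condom use, "a linear mixed effects model will be adopted with intervention group and baseline consistency of condom use as the covariates". The next sentence brings in the interaction: "The group by time interaction shall be assessed for changes of ICBI effects over time". The repeated visits are then mentioned in connection with the covariance: "The mixed effects model was to take account of the extra covariance of repeated measurements at 3 and 6 months". There is no model equation, no main effect of time is named, and the coding of time and group is not given.

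The description carries over to other outcomes. For the roughly continuous secondary outcomes, "the same analysis approach as mentioned above will be adopted"; for the dichotomous ones, "similar approach by a non-linear mixed effects model with a logit link will be used". On error rates: "Each estimated effect will be accompanied by a 95% confidence interval and 5% level of significance".

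The hypothesis in Section 5 covers both follow-up visits: "female students in the intervention group will have consistent condom use at 3- and 6-month follow-up compared to students in the control group".

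**The concern.** Taken literally, the fixed part of the model would hold group, baseline and group-by-time, with no term for time. An interaction fitted without that main effect does not measure a change in the intervention effect. With group as a 0/1 number, the control arm is forced to have the same mean at 3 and 6 months, and the interaction is simply the intervention arm's own change between visits. With group as a factor, it becomes a joint 2-df test of change in either arm. Both would reject when the two arms drift together and the intervention effect is constant.

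Shared drift is plausible here. Both arms answer the same questionnaire three times, and in the control arm "all participants will receive minimal intervention with a one-page online information about procedures and tips of condom use". Because the hypothesis names both visits, whether the effect lasts is part of what the trial may claim. A wrongly built interaction could report waning or growth that is not there, or miss a real change, and the same flaw would run through the secondary outcomes.

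**Working it through.** The plan gives no power calculation, SD, effect size or correlation, so it has no figure of its own to reproduce beyond the 5% level.

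**Inputs.** From the documents: n = 500 (Section 5, Subjects and setting); two follow-up visits and a 5% level (Section 9). Assumed: equal allocation, so 250 per arm; a two-sided test, to match the 95% confidence interval; complete data; baseline-adjusted SD of 1; between-visit correlation rho of 0.5 or 0.7; shared drift d = 0.1 SD from 3 to 6 months; constant intervention effect.

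**Time omitted, group as a 0/1 number (1 df).** The interaction estimates the intervention arm's change, with SE = sqrt(2(1 − rho)/250). The rejection rate is Phi(z − 1.96) + Phi(−z − 1.96), with z = d/SE.
- rho 0.5: SE = sqrt(1.0/250) = 0.0632, z = 1.58, rejection 35.3%.
- rho 0.7: SE = sqrt(0.6/250) = 0.0490, z = 2.04, rejection 53.2%.

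**Time omitted, group as a factor (2 df).** The statistic is chi-square on 2 df with noncentrality 2z².
- rho 0.5: noncentrality 5.0, rejection 50.4%.
- rho 0.7: noncentrality 8.33, rejection 73.6%.

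The coding of group decides between these two cases. With two visits, entering time as a number or as a factor makes no difference. In the 2-df case the model has one free mean per arm and visit, so its fitted means are those of the full model. The 3- and 6-month group differences from it are sound, and only the joint test is mislabelled.

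**Time included.** The interaction is the difference between the arms' changes, so shared drift cancels. Simulation (4,000 trials per setting, d = 0.1) gave 5.5% at rho 0.5 and 4.9% at rho 0.7. The same runs without time gave 35.6% and 53.4% (1 df), and 50.6% and 74.6% (2 df), in agreement with the formulas.

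**Sensitivity, time omitted.**
- No drift: 5% under either coding, so no harm.
- d = 0.05 SD: 12% to 23% over rho 0.5 to 0.7 and both codings.
- d = 0.1 SD, rho 0.3 to 0.8: 27% to 90% over both codings.
- d = 0.1 SD, 200 per arm, rho 0.5 to 0.7: 29% to 63% over both codings.

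**Main efficacy effect.** In the model without the interaction, the group coefficient compares the arms averaged over the two visits. A shift common to both arms cancels whether or not time is fitted. Simulated rejection with no intervention effect and a shared drift of 0.1 SD was 5.2% at rho 0.5 and 4.9% at rho 0.7.

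**Reading the text.** One sentence names group and baseline as covariates; a separate sentence adds group-by-time. The interaction is missing from the first sentence just as time is, yet it is plainly to be fitted. The first sentence is therefore not a complete list of terms, and the absence of time from it does not show that time is excluded. The stated aim of the interaction, to detect change in the intervention effect, is met only when the model also contains time.

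**The case for a change.** The strongest case for a change is that Section 9 is the whole analysis specification, it does name covariates, and time is not one of them. The consequence of a literal fit is algebra rather than opinion, and it runs both ways. If controls rose by 0.2 SD while the intervention arm stayed flat, the version without time and with group as a 0/1 number would reject only 5% of the time. With time included the SE is sqrt(4(1 − rho)/250) = 0.0894 (rho 0.5) or 0.0693 (rho 0.7), and power is 61% or 82%. A group coefficient read from a no-time interaction model could also be distorted by shared drift. The repair would cost one clause and one parameter.

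The algebra stands, and so does the observation that the description is incomplete. The step from an unnamed term to an omitted term does not. Fitting an interaction with its main effects is ordinary practice, and here the stated purpose requires it. The distortion of the group coefficient needs further choices that the plan does not make: group as a number, a particular numeric coding of months, and efficacy read from the interaction model. Complete data is a further assumption. Section 9 also plans to carry last values forward, and a carried-forward 3-month value shows no later change, which would dilute any drift.

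Whether one contrast, such as the average over 3 and 6 months, should be named the single primary test is a separate question of estimand and multiplicity. A missing time term does not raise it.

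**Conclusion.** No change is called for. Section 9 leaves a detail unstated, and any analyst fitting a group-by-time interaction would supply it by including visit as a main effect in the linear and logit models alike. The interaction test then holds about 5% under shared drift.

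The inflation of 35% to 74% at a drift of 0.1 SD is real only if time is actually left out. It also depends on a drift and a between-visit correlation (0.5 to 0.7) that the documents do not give, on 250 per arm and on complete data; with no drift it disappears. The common group effect from the model without the interaction, which is the efficacy test that Section 9 implies, is unaffected on either reading. Naming visit among the fixed terms would be harmless, but the trial's conclusions do not depend on it.
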